7.1.5 Vital Signs

Vital signs (body temperature, heart rate, respiration rate, and blood pressure) will be obtained at times specified in [Appendix A](#). Vital signs will be measured after resting at least 5 minutes. The pre-dose vital signs on days of dosing will be measured within 60 minutes of study drug dosing; Day 1 post-dose vital signs measurements should be taken within \pm 5 minutes of the 15-minute post-dose timepoint and within \pm 10 minutes for additional post-dose timepoints. Other vital signs during the inpatient stay will be taken within \pm 30 minutes of the nominal timepoint. For outpatient visits, vital signs will be measured within the visit window.

Day 1 post-dose timepoints for vital sign measurements for the IV portion of Part 3 will be based on the start of infusion.

7.1.6 Electrocardiograms

Standard 12-lead ECGs to assess heart rate, rhythm, and PR, QRS, QT, and QTc interval durations will be obtained at times specified in [Appendix A](#).

ECGs (triplicate readings, at least 1 minute apart within a 15-minute period), will be taken after at least 5 minutes in the supine position. The pre-dose ECGs on days of dosing will be taken within 60 minutes of study drug dosing. Post dose ECGs on days of dosing will be taken at 4 hours (\pm 10 minutes) after SC dosing. Post dose ECGs on days of dosing will be taken at 1 hour (\pm 10 minutes) from start of infusion for IV administration in Part 3.

ECGs will also be taken at the following timepoints:

- Day 7, Day 30, and Unscheduled visits for SAD
- Day 21, Day 30, Day 45, and Unscheduled visits for MAD
- Day 52 and Unscheduled visits for BA

The screening ECG will be used by the PI to determine a subject's eligibility for enrolment. The Day 1 pre-dose ECG will be reviewed to determine if subjects can be dosed.

All ECGs will be reviewed by the PI or designee. ECGs with the following readings will be considered acceptable for trial participation and will not be considered abnormal for trial purposes unless the PI or physician designee believes they represent a new medical condition when compared to baseline ECGs. In such cases an AE will be documented, and the subject will be followed for safety evaluations as appropriate. The following pre-existing conditions identified at enrolment will not be considered AEs:

- Sinus bradycardia,
- Sinus arrhythmia,
- Subjects without a history of prolonged QTc and an abnormal QTc interval at Screening will undergo repeat ECG assessment within the screening period before randomization to confirm prolongation. If the repeat ECG QTcF is within normal limits (see [Appendix B](#)) the subject may be considered for enrolment.

The Sponsor may review all or individual screening ECGs or may delegate to determine if meets intention of entry criteria goal of enrolling healthy normal subjects.

If a subject has possible cardiac-related symptoms, repeat ECGs will be obtained every 30 minutes (± 3 minutes) until the waveform reverts to its baseline appearance, or symptoms resolve, or are determined not to be cardiac-related. Subjects with cardiac-related symptoms that are associated with ECG changes will be transferred to appropriate emergency department for further evaluation and treatment at the discretion of the PI.

7.1.7 Assessment of Concomitant Medications/Treatments Other than Study Product

Subjects are required to abide by the following rules regarding intake of medications and other substances before and during the study:

- 1) Refrain from the use of any prescription medications (with the exception of hormonal contraceptives), within 14 days before the first study drug administration and until after the final study visit.
- 2) Refrain from the use of over-the-counter medications including vitamins, supplements, and herbal supplements (except for acetaminophen or ibuprofen) within 14 days before the first study drug administration,
- 3) The use of tobacco product, including smoking and the use of snuff and chewing tobacco, and other nicotine or nicotine-containing products (including patches), is not permitted by a subject within 90 days of Screening for the study or while a subject is enrolled in the study. A urine test for cotinine will be performed at Screening and upon admission to the CRU.
- 4) Refrain from consuming foods or beverages containing the following substances for the duration of the study:
- 5) Alcohol: ≤ 48 hours before the first study drug administration until discharge. A urine alcohol test will be performed at Screening and upon admission to the CRU.

- 6) Xanthines/caffeine: ≤24 hours before the first study drug administration and until discharge.
- 7) Refrain from receiving a live or killed vaccine, or immunoglobulin, within 14 days prior to dosing.
- 8) The use of illegal drugs is not permitted while a subject is enrolled in this study. A urine drug test will be performed at Screening and upon admission to the CRU.
- 9) Previous participation in this trial, any other rezafungin trial, or any trial involving administration of drug product within 28 days of study drug dosing. Plans to enroll in another clinical trial that could interfere with safety assessment of the investigational product at any time during the study period;

If a subject is unable to comply with the restrictions described above, the subject's continued participation in the study will be re-evaluated by the Investigator, in consultation with the Medical Monitor.

7.2 Laboratory Evaluations

7.2.1 Clinical Laboratory Evaluations

All laboratory assessments will be done by the clinical site's certified laboratory. Laboratory toxicity grading will be determined by use of the FDA Guidance for Industry: Toxicity Grading Scale for Healthy Adult and Adolescent Volunteers Enrolled in Preventive Vaccine Clinical Trials September 2007 and the Division of Microbiology and Infectious Diseases (DMID) Adult Toxicity Table November 2007, as modified for this study and appropriate for the administration of rezafungin ([Appendix B. Toxicity Grading Criteria for Normal Human Subjects](#)).

At Screening, laboratory test values that fall outside the reference range on the laboratory reports and deemed not clinically significant by the Investigator may be repeated at the discretion of the Investigator (to assess for transitional conditions). Laboratory values that fall outside of the reference range on Day -1 (baseline), may not be repeated, and subject will be withdrawn from the study. (See Note below for exceptions).

If a single repeat Screening evaluation is within the reference range, the subject may be further considered for study eligibility.

Note: Hematuria during active menses causing urinalysis results outside the reference range will not be considered clinically significant (not an AE).

Viral Serology Testing

Subjects will be screened for HIV antibody, hepatitis B surface antigen, and hepatitis C virus antibody. These tests must be negative for eligibility into this trial. In cases where a false positive result is suspected, confirmatory testing may be performed (e.g., Polymerase Chain Reaction).

Drug, Alcohol, and Cotinine Testing

The urine toxicology screen will be performed to detect the presence of amphetamines, barbiturates, cocaine, opiates, cannabinoids, phencyclidine, and benzodiazepines. The results must be negative for eligibility into this trial. A urine alcohol test will also be performed to detect alcohol use and must be negative prior to randomization. A urine cotinine test will also be performed to detect nicotine use and must be negative prior to randomization.

Follicle Stimulating Hormone (FSH) and Pregnancy Testing

For women of child-bearing potential, a serum pregnancy test will be done at screening and must be negative for eligibility into this trial. A serum pregnancy test will be done on Day -1, which must be reported as negative before dosing. A serum pregnancy test will be repeated at the final trial visit. Perform FSH test in postmenopausal females only, prior to randomization.

Safety Laboratory Tests

The following laboratory tests will be performed as specified in [Appendix A](#). Subjects will be fasting. This means no food or drink (other than water) for at least 8 hours before sampling.

- Hematology: complete blood count (CBC) with differential (red blood cell count, total and differential white blood cell counts, hemoglobin, hematocrit, and platelet count),
- Coagulation; (activated partial thromboplastin time [APTT], prothrombin time [PT}, and international normalized ratio [INR]),

- All subjects must undergo clinical chemistry testing (albumin, glucose, blood urea nitrogen or urea, potassium, calcium, sodium, chloride, total protein, creatinine, total carbon dioxide (CO₂), creatine phosphokinase (CK), phosphorus, alkaline phosphatase, aspartate aminotransferase (AST), alanine aminotransferase (ALT), total bilirubin, direct bilirubin at Screening and Baseline to assess protocol eligibility. Clinical chemistry tests will be performed thereafter as specified in the [Schedule of Assessments and Procedures Appendix A](#). Subjects must fast a minimum of 8 hours before blood collection for a clinical chemistry panel.
- Dipstick urinalysis: protein, blood, and glucose must be negative or trace (complete urinalysis to be performed if dipstick urinalysis is positive for blood). Menstruating females failing inclusion criteria due to a positive result may be retested following cessation of menses. Do not exclude subjects with >5 red blood cells/high power field if menstruating.

Laboratory values will be entered in the Clinical Labs eCRF.

7.2.2 Research Assays

Bioanalytical Assay

Plasma concentrations of rezafungin in EDTA will be determined by a validated LC-MS/MS method. Details are provided in the MOP for sample collection time in each cohort for SAD (except cohort 1), MAD, and BA.

For Part 1/SAD blood samples will be collected at the following scheduled timepoints for Cohorts 2, 3, 4, 5, and 6 (see Table 5). For Part 2/MAD, blood samples will be collected at the following scheduled timepoints for Cohorts 7, 8, 9, and 10 (see Table 6). For Part 3/BA, blood samples will be collected at the following scheduled timepoints for Cohort 11 (see Table 7).

Table 5: Blood Sampling Timepoints for Rezafungin Pharmacokinetic Analysis Cohorts 2, 3, 4, 5 and 6 SAD (Part 1)

Dosing Day	Timepoint						
Day 1 (pre-dose)	Taken within 60 minutes before study drug dosing						
Day 1 (hours post-dose)	0.5	1	2	4	6	8	12
Day 2 (hours post-dose)	24						
Day 3 (hours post-dose)	48						
Day 5 (hours post-dose)	96						
Day 7 (hours post-dose)	144						
Day 14	±1 Day						
Day 30	±1 Day						

Table 6: Blood Sampling Timepoints for Rezafungin Pharmacokinetic Analysis Cohorts 7, 8, 9, and 10 MAD (Part 2)

Dosing Day	Timepoint						
Day 1, 8, and 15 (pre-dose)	For Day 1 taken within 60 minutes before study drug dosing and for Days 8 and 15, taken within 15 minutes before study drug dosing						
Day 1 and 15 (hours post-dose)	0.5	1	2	4	6	8	12
Day 2 and 16 (hours post-dose)	24						
Day 3 and 17 (hours post-dose)	48						
Day 5, 12, and 19 (hours post-dose)	96						
Day 7, 14, and 21 (hours post-dose)	144						
Day 8 (hours post dose)	1 and 4	1		4			
Day 30	±1 Day						
Day 45	±1 Day						

Table 7: Blood Sampling Timepoints for Rezafungin Pharmacokinetic Analysis Cohort 11 BA (Part 3)

Dosing Day	Timepoint						
Day 1 and 22 (pre-dose)	Taken within 60 minutes before study drug dosing						
Day 1 and 22 (hours post-dose*)	0.5	1	2	4	6	8	12
Day 2 and 23 (hours post-dose*)	24						
Day 3 and 24 (hours post-dose*)	48						
Day 5 and 26 (hours post-dose*)	96						
Day 7 and 2 (hours post-dose*)	144						
Day 14 and 35	±1 Day						
Day 52	±1 Day						

*Post-dose timepoints for PK blood sampling for the IV portion of Part 3 will be based on the start of infusion

Laboratory Specimen Preparation, Handling, and Storage

Detailed instructions for plasma and urine for drug testing and urinalyses specimen preparation, handling and storage are outlined in the MOP for this study.

Total Blood Volume Drawn

The total volume of blood that will be drawn from each subject is described in Table 8:

Table 8: Total Volume of Blood Drawn From Each Subject - Part 1 (SAD) Cohorts 1-6

Laboratory Test	Sample Volume (mL)	Number of Samples	Total Volume (mL)
Safety:			
Clinical chemistry	4	5	20
Hematology	2	5	10
Coagulation	2.7	5	13.5
Serology	4	1	4
Pharmacokinetic: [*]	3	14	42
When using an indwelling catheter 1.0 mL of blood will be removed prior to sample collection			
Total	15.7	30	89.5
Cohort 1 Total*	12.7	16	47.5

*No PK blood samples collected in Cohort 1.

Table 9: Total Volume of Blood Drawn From Each Subject - Part 2 (MAD) Cohorts 7-10

Laboratory Test	Sample Volume (mL)	Number of Samples	Total Volume (mL)
Safety:			
Clinical chemistry	4	9	36
Hematology	2	9	18
Coagulation	2.7	9	24.3
Serology	4	1	4
Pharmacokinetic:			
	3	27	81
When using an indwelling catheter 1.0 mL of blood will be removed prior to sample collection			
Total	15.7	55	163.3

Table 10: Total Volume of Blood Drawn From Each Subject - Part 3 (BA) Cohort 11

Laboratory Test	Sample Volume (mL)	Number of Samples	Total Volume (mL)
Safety:			
Clinical chemistry	4	7	28
Hematology	2	7	14
Coagulation	2.7	7	18.9
Serology	4	1	4
Pharmacokinetic:	3	27	81
When using an indwelling catheter 1.0 mL of blood will be removed prior to sample collection			
Total	15.7	43	145.9

Laboratory PK Specimen Shipping

All PK specimens will be shipped to the Fisher Biorepository for storage and/or transfer to the ICON ABL. Detailed instructions for shipping plasma are outlined in the MOP for this study.

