
Subjects will be admitted to the CRU on the day before injection (or infusion for Part 3) and the following procedures will be performed:

- On admission to the CRU on Day-1, review inclusion/exclusion criteria to ensure the subject is eligible for enrollment. For Part 3, Day 21, review inclusion criteria numbers 2-7 and 10-11, and exclusion criteria numbers 2-4 and 8-18 (from [Section 5.1.2](#)) to ensure the subject remains eligible for dosing.
- Update medical history.
- Review and update concomitant medications.
- Perform targeted PE.

- Obtain resting vital signs after being at rest for at least 5 minutes.
- Obtain weight, calculate BMI.
- Obtain blood samples for baseline fasting (at least 8 hours) clinical chemistry, hematology, coagulation tests, serum pregnancy test [if female of childbearing potential]); for the Day -1 visit, if clinical chemistry, hematology or coagulation test result(s) are outside of the reference range(s), they may not be repeated; if a result is not considered by the site investigator to be clinically insignificant, the subject is removed from the study.
- For women of child-bearing potential, perform a serum pregnancy test (results must be confirmed negative before dosing).
- Obtain blood and urine samples for safety clinical labs.
- Obtain urine sample for drug screen and urine alcohol.
- Obtain urine sample for cotinine test.
- Part 3 (Cohort 11) only, Day 21 – review Memory Aid.

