- j. ECGs will be obtained at Screening and on Day 1 within 60 minutes prior to study drug administration, and 4 hours (± 10 minutes) post-dose (SC) and 1 hour (± 10 minutes) post-dose (IV) from start of infusion for IV admin, Day 52, and Unscheduled visits
- k. Fasting (at least 8 hours) blood samples will be collected for hematology, coagulation and chemistries at Screening and on Days -1, 2, 7, 23, 28, and 52 (± 1 day). Hematology tests consist of CBC with differential; coagulation tests consist of PT/PTT/INR; Chemistries panel includes albumin, glucose, blood urea nitrogen or urea, potassium, calcium, sodium, chloride, total protein, creatinine, CO₂, CK, phosphorus, alkaline phosphatase, AST, ALT, total bilirubin, direct bilirubin,
- l. Urine will be collected for urinalysis, urine drug screen and urine alcohol at Screening, and on Day -1. Urine will be collected for urinalysis on Days 2, 7, 23, 28, and 52 (± 1 day),
- m. Blood for PK analysis (plasma) will be drawn pre-dose within 60 minutes before study drug dosing and at 0.5(± 5 min), 1, 2, 4, 6, 8, and 12 hours (± 10 min) on Days 1 and 22; 24 hours (± 30 min), on Days 2 and 23; 48 hours(± 30 min) on Days 3 and 24; 96 hours (± 30 min), on Days 5 and 26; and 144 hours (± 30 min) on Days 7 and 28 after dosing; and on Days 14 and 35 (± 1 day) and 52 (± 1 day),
- n. Injection site assessment pre-dose and at 1 and 4 (± 10 min), 24, 48, 72, 96, 120, and 144 h (± 30 min) post-dose, Day 14 (± 1 day), and Day 35 (± 1 day). Unscheduled visits are not timed.
- o. Subjects are to be assessed for AEs occurring from the time of the first dose of study drug through Day 52 (± 1 day),
- p. Counsel/reminder on contraceptive use and post-discharge instructions (dietary and medication/nonmedication, vaccine and blood/blood product/sperm donation restrictions); as described in **Section 5.1**.
- q. Memory Aid issued on Day 1, training on Day 7 (refresher on Day 28), reviewed on Days 21, 14, 35, 52 and at Unscheduled visits.

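### Protocol Table 9 understates Part 2 blood sampling (27 PK samples against 31 scheduled), and the protocol contradicts itself on Part 3 Day 21 safety laboratory draws

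*Protocol*

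**What the plan says.** **Part 2.** Protocol Section 7.2.2 gives the sampling times under "Table 6: Blood Sampling Timepoints for Rezafungin Pharmacokinetic Analysis Cohorts 7, 8, 9, and 10 MAD (Part 2" and the blood budget under "Table 9: Total Volume of Blood Drawn From Each Subject - Part 2 (MAD) Cohorts 7-10". The budget's PK row is 3 mL × 27 samples = 81 mL, and its total is 55 samples and 163.3 mL. Footnote m of Table 12 (Appendix A) restates the PK schedule.

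**Part 3.** The heading of Section 6.3 covers admission on Day -1 and, for Cohort 11, on Day 21 as well. Its list includes: "Obtain blood samples for baseline fasting (at least 8 hours) clinical chemistry, hematology, coagulation tests". The Table 13 grid marks hematology, coagulation and chemistry in the column headed for both days. Footnote k of the same table places these bloods for "chemistries at Screening and on Days -1, 2, 7, 23, 28, and 52", with no Day 21. Table 10 budgets 7 safety draws and 27 PK samples, and prints a total of 43 samples and 145.9 mL.

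**Baseline.** Protocol Section 10.5.2 defines the laboratory baseline as the last result before the dose, taken separately for each treatment in the crossover.

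**Catheter discard.** Tables 8 to 10 each note that 1.0 mL is removed before a sample is taken through an indwelling catheter. None of the totals includes it.

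**The concern.** The Part 2 budget and the Part 2 schedule sit in the same section and disagree by four samples per subject. The budget is the lower of the two. Section 7.2.2 presents these tables as the total blood drawn from each subject, and the protocol is what the IRB reviews, so the stated volume is too small.

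The Part 3 conflict concerns more than volume. If no bloods are taken on Day 21, the last scheduled laboratory result before the Day 22 dose is Day 7: 144 h after the first dose and 15 days before the second. Section 10.5.2 calls a laboratory abnormality treatment-emergent by comparing its grade with baseline. A Grade 1 value on Day 7, possibly caused by the first treatment, would then stop a Grade 1 value after the second treatment from counting as emergent. Whether period 2 has a clean laboratory baseline therefore depends on which provision the site follows.

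**Working it through.** **Formulas.** A safety draw is chemistry 4 mL + hematology 2 mL + coagulation 2.7 mL = 8.7 mL, in three samples. Serology is one 4 mL sample. A PK sample is 3 mL. With s safety draws and p PK samples:

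- volume = 8.7 × s + 4 + 3 × p
- samples = 3 × s + 1 + p

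**Step 1. Reproduce the printed totals from each table's own rows.**

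| Table | s | p | Samples: computed / printed | mL: computed / printed |
|---|---|---|---|---|
| 8 (Part 1) | 5 | 14 | 30 / 30 | 89.5 / 89.5 |
| 8 (Cohort 1) | 5 | 0 | 16 / 16 | 47.5 / 47.5 |
| 9 (Part 2) | 9 | 27 | 55 / 55 | 163.3 / 163.3 |
| 10 (Part 3) | 7 | 27 | **49 / 43** | 145.9 / 145.9 |

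The formulas recover every figure except Table 10's sample total: its rows give 7 + 7 + 7 + 1 + 27 = 49.

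**Step 2. Count the Part 2 PK samples in Table 6.**

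- Row "Day 1, 8, and 15 (pre-dose": 3
- Row "Day 1 and 15 (hours post-dose": 7 times × 2 days = 14
- Row "Day 2 and 16 (hours post-dose": 2
- Row "Day 3 and 17 (hours post-dose": 2
- 96 h on Days 5, 12 and 19: 3
- 144 h on Days 7, 14 and 21: 3
- Day 8 at 1 h and 4 h: 2
- Days 30 and 45: 2

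Sum: 3 + 14 + 2 + 2 + 3 + 3 + 2 + 2 = 31. Table 12 footnote m gives the same 31. Counted the same way, Table 5 gives 14 and Table 7 gives 27, matching Tables 8 and 10. Only the Part 2 PK count fails.

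**Step 3. Part 2 total.** Table 12 footnote k lists 9 safety draws (Screening and Days -1, 2, 7, 9, 14, 16, 21 and 45), which agrees with Table 9.

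- PK volume: 31 × 3 = 93 mL
- Total: 9 × 8.7 + 4 + 93 = 175.3 mL
- Samples: 27 + 1 + 31 = 59
- Difference: 175.3 − 163.3 = 12.0 mL; 12.0 / 163.3 = 7.3%

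Sensitivity: Section 6.5.1 does not clearly name a Day 15 pre-dose sample. Leaving it out gives 30 PK samples and 78.3 + 4 + 90 = 172.3 mL, still above the printed figure.

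**Step 4. Part 3 on each reading.**

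| Reading | s | Samples | mL |
|---|---|---|---|
| Footnote k, no Day 21 draw | 7 | 21 + 1 + 27 = 49 | 60.9 + 4 + 81 = 145.9 |
| Section 6.3 and grid, with Day 21 draw | 8 | 24 + 1 + 27 = 52 | 69.6 + 4 + 81 = 154.6 |

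The difference is 8.7 mL (8.7 / 145.9 = 6.0%). Neither reading gives 43 samples.

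**Step 5. Catheter discard.** The number of catheter samples is not stated. As an upper bound for PK sampling in Part 2, if all 31 samples used a catheter, 31 × 1.0 = 31 mL would be added.

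**The case against.** The four-sample mismatch in Part 2 is not open to serious dispute. The rest can be challenged.

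*Does Table 10 simply omit a required draw?* A reader might infer so from Section 6.3 and conclude that 154.6 mL is the correct total. The documents do not support going that far:

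- Table 13 footnotes e, h, i, k and l (pregnancy test, vital signs, physical examination, bloods, urine) all list Day -1 and none lists Day 21. Footnote k is not an isolated slip.
- The Day 21 eligibility re-check in Section 6.3 covers exclusion criteria 2-4 and 8-18, so it skips criterion 6, out-of-range laboratory values.
- Section 7.2.1 attaches the word baseline to the Day -1 laboratory values and refers to Appendix A for timing, and Appendix A is itself divided.

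Against that stand the Section 6.3 heading and list, the Table 13 grid and the separate-baseline rule. Section 6.3 limits its no-repeat rule to the Day -1 visit. That can mean bloods are also taken on Day 21, or that only Day -1 bloods were in mind. The conflict stands; which side is right does not follow.

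*Were participants told too low a volume?* A reader might infer this, but the consent form is not available for review and Protocol Section 9.2 does not say that a blood volume is quoted. The inference cannot be made.

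*Is the effect trivial?* The amounts are 12 mL over 45 days and, conditionally, 8.7 mL over 52 days. The documents set no blood-volume limit, so none is shown to be exceeded. No estimate or halting rule uses the Table 9 total. SAP Section 1 states that no MAD or BA subject was enrolled, and Table 8, the only table that applied to enrolled subjects, reproduces. All of this stands and limits the consequence. It does not make the printed figures right.

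**Conclusion.** The point holds in two parts of different strength.

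- **Part 2, firm.** Table 9 is wrong and low. The schedule gives 31 PK samples, 59 samples in all and 175.3 mL, against 27, 55 and 163.3 mL (+12 mL, +7.3%). This rests only on counting Table 6 and on Table 9's own volumes per sample. No reading of the schedule gives 27. That number equals the Part 3 count, but a carry-over cannot be shown.
- **Part 3, a contradiction to be resolved.** The provisions disagree on Day 21 safety bloods, and the period-2 laboratory baseline depends on the answer. The total is 145.9 mL or 154.6 mL accordingly. The printed 43 samples is wrong under both.

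All totals exclude catheter discard. No collected data and no analysis in the SAP are affected; the correction matters for the protocol of record and for any reuse of the design.

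**What to change.** 1. Table 9: change the PK row to 31 samples and 93 mL, and the total to 59 samples and 175.3 mL.
2. Make Section 6.5.1 say explicitly whether a Day 15 pre-dose PK sample is taken, as Table 6 and Table 12 footnote m have it.
3. Reconcile Section 6.3, the Table 13 grid, footnote k and Table 10 on Day 21 safety bloods, and check footnotes e, h, i and l at the same time. In Section 10.5.2, state which result is the period-2 laboratory baseline.
4. Set Table 10 to match the decision: 49 samples and 145.9 mL for 7 draws, or 52 samples and 154.6 mL for 8.
5. State under Tables 8 to 10 that catheter discard is additional to the totals.
6. Check any blood volume quoted in the consent form against the corrected totals.

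The cost is table and footnote wording, plus consent wording if a volume is quoted there. The stated Part 2 volume becomes slightly less favourable, and the Part 3 volume does too if the Day 21 draw is confirmed.
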